#### 4.2.2 Analysis Methods

##### Within-participant HSV-2 DNA detection rate on days with asymptomatic shedding

If the difference between the number the number of swabs on which shedding occurs only pre-intervention and the number of swabs on which shedding occurs only post-intervention averages above zero, it indicates that the detection rate is decreased following intervention, and therefore a protective effect of the intervention with regard to shedding. Since this number is not distributed according to a known distribution, it will be compared to zero using the non-parametric Wilcoxon signed-rank test.

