Background	
Genital herpes has a high prevalence in industrialized as well as developing countries.
 
Genital herpes causes genital ulcers, increases risk for acquiring HIV infection, and may be transmitted mother to child during birth with possible serious consequences.
 
Medical treatments and condoms only partially reduce the risk for transmission from/ to sexual partners. Genital herpes transmission despite use of condoms is thought to be due to transfer via skin-to-skin contact in unprotected areas, and HSV-2 transmission may be enhanced by current shaving habits in the genital area leading to micro lesions (lacerations) of the skin.
 
VIBLOK™ is a cream designed to impede the passage of viruses, such as HSV-2, across the skin. Bench and animal experiments indicate that it can block virus transmission (HIV, HPV, HSV) up to 98%.
 
The objective of this clinical trial is to assess the safety and performance of VIBLOK in adults with HSV-2 infection by comparing virus detection in the extra-genital area before and after application of the barrier cream.

Primary objective	To assess safety of VIBLOK in HSV-2 infected adults.
Secondary objective	To evaluate the performance of VIBLOK as a barrier for virus transmission in men and women.
Study design	The VIBLOK SAfety and perFormancE Trial is a prospective, non-randomized, comparative multi-center safety and performance study. Up to 84 adults with a suspected HSV-2 infection are planned to be enrolled at up to 6 participating investigational centers in The Netherlands and Germany. Participants with a confirmed HSV-2 infection are planned to be followed for 26-31 days, using VIBLOK for minimally 26 days in a row. Safety will be assessed by collecting all adverse events, and HSV will be measured from daily self-collected external genital swabs before and after application of VIBLOK.
Study device	VIBLOK cream
Study scope	Minimally 1 and maximally 6 sites in The Netherlands and Germany are

	planned to participate in this study.
Study duration	The study is anticipated to last 12 months from first-subject-in to last-subject-out. Study participants are planned to be followed for 26 to 31 days.
Study Population	Adults with recurrent genital HSV-2 infections that meet all the inclusion and none of the exclusion criteria.
Number of subjects	Up to 84 men and women are to be enrolled, ensuring 46 participants with confirmed eligibility applying VIBLOK.

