After the examination, the participant will receive instructions by the site research staff as to how to take swabs and to apply VIBLOK, watch the instruction video, and subsequently takes the first swab, applies VIBLOK, and takes a second swab 5-60 minutes after applying VIBLOK while at the research site. These procedures will be monitored by one person from the site research staff to ascertain that the cream was applied correctly and that the swabs were obtained in the right way. Participants will also be instructed in how to label the swabs and vials. Once the swabbing procedures are correctly done, the participant will be provided the following:

- The study device along with instructions for use;
- The swabbing kits along with instructions for use;
- Diary.

Participants with a negative HSV-2 serology will be considered screen failures and exit the study.

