Appendix 1: English master Informed Consent

Appendix 2: Daily Home PCR Instructions for Women

Thank you for volunteering for this study. Please read this sheet over carefully to understand how the study is being done.

Study Supplies

You will receive the following supplies:

- Dacron-tipped swabs (similar to Q-Tips®)
- Small plastic vials (with green, yellow, and red labels)
- Color coded labels
- A storage box
- VIBLOK cream
- Mirror
- A bag for transport
- A swab collection log
- A study diary

Sample Labels

The labels are preprinted with your study, clinic, and participant number. For each sample you collect, please fill in the date and time you collected the sample.

Study Diary

It is important that you bring your study diary to **each** clinic visit. Fill out the diary immediately before you obtain your swab samples. Please record this information as accurately as possible.

Storage of Samples

Vials with and without swabs can be stored at room temperature. When you return to the clinic for your next appointment, please bring the storage box with all the swab samples and your diary.

Communicating with the Clinic

If you develop symptoms of a recurrence or have any questions, please contact the **<specify the department>**. If you have ANY unusual urinary, genital, or rectal symptoms, such as a urinary tract infection, rash, or bleeding, call the clinic as soon as possible for an appointment. Every effort will be made to accommodate your schedule for clinic visits. Please call in at the earliest sign of symptoms so that a visit can be scheduled as soon as possible.

Weekdays: <specify contact information>

After Hours: <specify contact information>

Collecting Daily Swab Samples

Please read the following instructions carefully, it is very important that you collect samples in the same order as given in the instructions.

Please collect two extra-genital swabs per day: one **before** and one 5-60 minutes **after** VIBLOK application.

Please also collect a swab from a herpes **lesion** during an outbreak: do not apply VIBLOK when you develop a lesion and contact the clinic when you first notice symptoms.

Collect samples **once a day** before bathing or showering, or at least one hour after bathing or showering. Thoroughly wash and dry your hands before beginning.

[figure not shown]

Figure 2.1. Female genitals with VIBLOK application and swabbing area.

1/ To collect the **EXTRA GENITAL swab in the **green-labeled vial** **before** VIBLOK:**

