1. Unwrap 1 sterile swab and hold it by the plastic shaft. Try not to touch the Dacron tip with your hands.

2. Gently put the swab on your labia.
3. Rotate the swab in a full circle. Gently remove the swab from your labia.
4. Rub the same swab from the outer (hairy) edges of your labia to the smooth skin below the vaginal opening, covering the entire area.
5. Rub the swab over the skin between your vagina and anal opening (anus).
6. Rub the swab in a circular motion over your rectal area, covering a radius of about 1.0 cm around the anus.

2/ Closing the vials and labeling:

1. Place the collected swab into the vial with the **green color coded** label.

2. Pull the swab out of the vial 0.5 cm, break (or cut) off the end of the plastic shaft, and discard it in the trash.
3. Securely replace the screw top of the vial.
4. Complete the swab collection log, with the full date (for example: 17-AUG-2015) and time of collection.
5. Place the labeled vial inside the grid box.

3/ Apply VIBLOK

1. Apply one packet of VIBLOK™ evenly and thoroughly to all external genital (including labia and clitoris), pubic, and perianal areas with or without hair.
2. Ensure application from minimally 2 cm outside of the outer (hairy) edges of your labia to the smooth skin below the vaginal opening, covering the entire area, the skin between your vagina and anal opening (anus), and your rectal area, covering a radius of about 2.5 cm around the anus. Apply more than one packet if needed.
3. Wait 5 to 60 minutes.

4/ To collect the **EXTRA GENITAL** swab in the **yellow-labeled** vial after VIBLOK:

1. Repeat the procedure as described under 1/ and 2/ using the vial with the **yellow color coded label**
2. Make sure to rub the swap only in the area where you applied VIBLOK: Keep a distance of at least 1 cm to the outer edges.
3. Use the mirror from your sampling kit if needed.

5/ To collect a **LESION** swab in the **red-labeled** vial:

If you develop a herpes lesion, please rub a separate swab over this area and place the swab in one of the **red-labeled** vials. Do **not** apply VIBLOK when you develop a herpes lesion and call the clinic when you first notice symptoms.

Repeat the procedure as described under 2/.

6/ After collection of the swabs

After you have collected the daily swabs, ensure to

1. thoroughly wash and dry your hands
2. have completed the participant diary

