#### 1.4 Sample size justification

The primary endpoint is the SADE incidence at 28 days of VIBLOK usage.

With a sample size of 36, an exact two-sided 95% confidence interval for a single proportion will show that the SADE incidence is below 10% at an expected incidence of 0.1%. Taking into account a drop-out rate of 15%, the estimated sample size needed is 42 study participants applying the VIBLOK cream.

The secondary endpoint is VIBLOK performance.

Statistical analysis will evaluate whether the disagreement rate in positivity between the pre and post-treatment swabs is indicative of a decrease in detection frequency. For each person, the number of swabs on which shedding occurs only pre-intervention will be assessed, and then the number of swabs on which shedding occurs only post-intervention will be subtracted.

If this number averages above zero, it indicates that the detection rate is decreased following intervention, and therefore a protective effect of the intervention with regard to shedding. Since this number is not distributed according to a known distribution, it will be compared to zero using a non-parametric test, the Wilcoxon signed-rank test. With an 8% anticipated asymptomatic shedding rate, 80% power and type I error of 5%, 40 participants taking samples for 28 days are needed to show a 50% reduction post-intervention, i.e. after applying VIBLOK.

Taking into account a drop-out rate of 15%, up to 46 adults applying VIBLOK cream are needed.

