##### HSV-2 copy number on HSV DNA positive samples detected by quantitative real-time

The difference of the mean PCR HSV-2 copy number on days with asymptomatic shedding occurring only pre-intervention and occurring only post-intervention will be compared to zero using the non-parametric Wilcoxon signed-rank test.

Both analyses will be based on the As Treated Population and repeated for the Per Protocol Population.

Exploratory Poisson regression analyses may also be performed exploring the effect of other covariates like center, age and gender.

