### 4.3 Exploratory Endpoints

#### 4.3.1 Definition

Sub-analyses will be performed as follows:

- To explore VIBLOK's blocking ability in relation to

Gender

Between gender differences will be assessed for the secondary efficacy endpoints.

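### Every swab pair is taken in the order swab, cream, swab with no cream-free pair or recovery control described, so lower detection on the second swab cannot be read as a protective effect of the cream on shedding

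*SAP*

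**What the plan says.** At Visit 1 the participant "takes the first swab, applies VIBLOK, and takes a second swab 5-60 minutes after applying VIBLOK" (Protocol 5.2.3). The same sequence is followed daily at home, where participants are told that "it is very important that you collect samples in the same order as given in the instructions" (Protocol Appendix 2; Appendix 3 gives men the same instruction). For swab 2 the instruction is "Repeat the procedure as described under 1/ and 2/ using the vial", this time with the yellow label and staying within the creamed area. SAP 1.5 describes the study as single-arm and open-label, without randomization.

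The detection-rate endpoint counts, per participant, the swabs positive only before cream minus those positive only after. This is compared with zero by the Wilcoxon signed-rank test. SAP 4.2.2 interprets a mean above zero as follows: "it indicates that the detection rate is decreased following intervention, and therefore a protective effect of the intervention with regard to shedding". SAP 1.4 and Protocol 9.1 also conclude "and therefore a protective effect of the intervention with regard to shedding".

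Two other analyses use the same ordered pairs. One is the copy-number comparison, defined as "The difference of the mean PCR HSV-2 copy number on days with asymptomatic shedding occurring only pre-intervention and occurring only post-intervention". The other is the set of sub-analyses in SAP 4.3, introduced as "To explore VIBLOK's blocking ability in relation to".

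**The concern.** Lower detection on swab 2 is something the data can show. Attributing it to the intervention is a further step, and the design described does not support it. Three things change together between the swabs: cream has been applied, the skin has already been swabbed once, and the second swab is taken through a silicone and zinc oxide cream (Protocol 2.1) that might change how much DNA is picked up or amplified. The signed-rank test sees only their sum.

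The secondary objective in the synopsis is "To evaluate the performance of VIBLOK as a barrier for virus transmission in men and women", and Protocol 1.1 says performance data will be submitted for CE marking. Detection rate and copy number are the only performance endpoints with a stated hypothesis (SAP 1.3). If the pre-specified text already equates a positive difference with protection, the report may carry that reading into the file without the qualification it needs.

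**Working it through.** **1. What would be needed to separate the explanations, and whether it is described**

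| Explanation for fewer positives on swab 2 | What would isolate it | In the protocol or SAP? |
|---|---|---|
| Effect of the cream | Comparison with pairs taken without cream | Not described |
| Removal of virus by swab 1 | Cream-free or reversed-order pairs | Not described |
| Poorer pick-up or PCR recovery through cream | Recovery control with known DNA and cream | Not described; Protocol 9.6 and 10.4 say only that a core laboratory analyses the swabs |

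The timing graph in SAP 4.3.2 plots the pre/post difference against the time of the post-cream sample. It has no cream-free reference, so it does not fill the gap. The lesion swab is separate and unpaired.

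**2. Expected net difference**

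Inputs from SAP 1.4: 8% detection, 28 days, 50% reduction.
- Expected positive first swabs per person: 0.08 × 28 = 2.24.
- Planned cream effect of 50%: 2.24 × 0.50 = 1.12 net swab-days.
- Inert cream, 50% loss on swab 2 from order or recovery: 2.24 × 0.50 = 1.12.
- Inert cream, 10% loss: 0.224. With 20% loss: 0.448.

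The same size of reduction gives the same expected value of the test variable whatever its cause.

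**3. The plan's sample size of 40**

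The plan does not state the between-person variance or the agreement between paired swabs, so 40 can be reached but not confirmed. In simulation (beta-distributed person rates, signed-rank test with zeros dropped, normal approximation, two-sided 5%), power for a 50% reduction at 40 participants was:
- 97-100% at intraclass correlation 0-0.5 if swab 2 can be positive only when swab 1 is (full agreement);
- 82-97% over the same range if the swabs are independent given the person's rate.

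Power near 80% is reached at an intraclass correlation of about 0.65-0.7 with full agreement, or 0.55-0.6 with independence.

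**4. How often an inert cream would look protective**

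Settings: 40 participants, 28 days, 8% first-swab detection, no cream effect, swab 2 detection multiplied by (1 − loss). Only settings near 80% power for a 50% reduction are used. The losses, swab agreement and between-person spread are assumptions; none is in the documents. Entries are the share of simulated trials with two-sided p < 0.05 and a positive difference.

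| Agreement of the two swabs | 10% loss | 20% loss |
|---|---|---|
| Independent given the person's rate | 10-14% | 29-33% |
| Shared shedding days, per-swab sensitivity 0.9 | 17-27% | 45-60% |
| Full agreement, no continuity correction | about 39-46% | about 60-68% |
| All settings examined, including sensitivity 0.6-0.95 | roughly 9-46% | roughly 29-68% |

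With no loss the figure is about 2.5% or less. The spread comes mainly from swab agreement and between-person variance, and also from the continuity correction. The effect on copy number was not quantified.

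**The case against.** - **The sentence is limited to shedding and is not a decision rule.** It explains the sign of a mean. The hypotheses in SAP 1.3 are neutral and two-sided, and no performance success criterion exists. This is correct, and it makes the overreach narrower than a claim of blocked transmission. But the sentence still credits the intervention with an effect, and the analysis serves an objective framed as barrier performance.
- **No bias has been shown.** Also correct. A reader might infer that the pairs are known to favour the cream, or that a positive result would be false. The documents do not support that: they give no loss size, and continued shedding between swabs, or spreading of virus while cream is applied, could raise detection on swab 2 and mask a real effect.
- **A laboratory control may exist.** A reader might infer that none was run. All that can be said is that the protocol and SAP describe none. The Investigator's Brochure and core-laboratory procedures were not available. Such data could address recovery through cream, but not removal by swab 1.
- **The design is openly single-arm, and the report could state the limitation.** It could, but the pre-specified text currently says the opposite, and wording agreed before results are known carries more weight.
- **The simulated ranges are conditional.** They are. They show that a modest loss could matter; they do not estimate what will happen in this trial.

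**Conclusion.** The concern stands as a point about interpretation. Under the procedures described, a positive mean difference establishes lower HSV-2 DNA detection on swab 2 and nothing more specific, so attributing it to the cream in SAP 4.2.2, SAP 1.4 and Protocol 9.1 is unsupported. The copy-number comparison and the SAP 4.3 sub-analyses share the limitation.

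This conclusion rests on the fixed order and the absence of a described control, not on the simulation. The illustrative frequencies depend on assumed losses and on correlation and variance that the plan does not give, so they are not bounds.

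It would go too far to conclude that the trial's success is in doubt. Success is defined only by the upper confidence limit for SADE incidence being below 10% (SAP 1.3 and 5.2.1), which does not use the swabs. Because the performance results are secondary but intended for the CE-mark submission, the wording should be fixed.

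**What to change.** In SAP 4.2.2 and SAP 1.4 now, and in Protocol 9.1 at the next amendment, replace the clause that infers a protective effect with:

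*that is, lower HSV-2 DNA detection on the second swab, which may reflect the cream, removal by the preceding swab, reduced DNA recovery in the presence of cream, or a combination; a significant result alone does not establish a barrier effect.*

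Apply the same caveat to the copy-number comparison (SAP 4.2.1 and 4.2.2) and state once that it covers the SAP 4.3 sub-analyses. Cite any existing recovery data for cream-coated swabs.

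The SAP edit can be made before database lock. The protocol edit needs the written agreement, signatures and, if required, ethics committee approval set out in Protocol 11.6. Data collection, test, sample size and participant burden do not change. The cost is a less favourable performance statement for the CE-mark file.

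This corrects the interpretation only and does not remove the confounding. Cream-free pairs would address removal by swab 1 but not recovery through cream, and the sample size would have to be re-derived.

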##### HSV-2 copy number on HSV DNA positive samples detected by quantitative real-time

The difference of the mean PCR HSV-2 copy number on days with asymptomatic shedding occurring only pre-intervention and occurring only post-intervention will be compared to zero using the non-parametric Wilcoxon signed-rank test.

Both analyses will be based on the As Treated Population and repeated for the Per Protocol Population.

Exploratory Poisson regression analyses may also be performed exploring the effect of other covariates like center, age and gender.

### 4.3 Exploratory Endpoints

#### 4.3.1 Definition

Sub-analyses will be performed as follows:

- To explore VIBLOK's blocking ability in relation to

Gender

Between gender differences will be assessed for the secondary efficacy endpoints.

#### Time between VIBLOK application and sampling

- The timing of the post VIBLOK sample in relation to the difference between the pre and post VIBLOK HSV-2 sample values

#### Shaving and waxing habits

- The genital grooming habits in relation to the pre-VIBLOK HSV-2 sample value.
- The genital grooming habits in relation to the difference between the pre and post VIBLOK HSV-2 sample value
- Participant satisfaction using VIBLOK as assessed on the participant questionnaire
  - Ease of use of VIBLOK (Very easy to use / Somewhat easy to use / Difficult to use)
  - The use of VIBLOK (Simple and clear / Somewhat confusing / Very confusing)
  - VIBLOK user documentation (Excellent / Adequate / Inadequate)
  - Use of VIBLOK if VIBLOK was available for use (Participant would use it / Participant would use it only in very special cases / Participant would never use it)
  - The best participant liked about VIBLOK
  - The least participant liked about VIBLOK
  - Suggestions of participant for improving VIBLOK
- Symptoms (Itching, burning, tingling / Lesions (sores, blisters, ulcers, crusts) / Other) as recorded on the participant's diary.
- Location of the lesion (Genitals / Rectal (perineum, perianal) / Buttock / Other) as recorded on the participant's diary.

#### **4.3.2 Analysis Methods**

- To explore VIBLOK's blocking ability in relation to

#### Gender

Between gender differences will be assessed for the secondary efficacy endpoints using the Wilcoxon rank-sum test. Hodges-Lehmann estimates (point estimate and 95% exact confidence interval) will be used to assess the location of the shift between males and females.

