3.3. Exploratory Parameters

- Sub-analyses to explore relation of device performance to
 - Gender
 - Time between VIBLOK application and sampling
 - Shaving and waxing habits
 - HSV symptoms
- Participant satisfaction using VIBLOK as assessed on the participant questionnaire (appendix 5).

4. Study Population

Participants will be screened and selected from men and women with a (suspected) HSV-2 infection.

For the sake of the sub-analysis on a possible relation of device performance to gender, an effort will be made to enroll an equal amount of men and women. Therefore enrolment will be tracked to ensure enrolment of a minimum of 16 participants of the less represented sex.

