5.2.6. Genital herpes recurrence – Unscheduled visits

If a lesion develops that is consistent with genital herpes, swabs should be obtained from the lesion. Participants who have such a recurrence (i.e., papules, vesicles or pustules, ulcers, or crusts) during the treatment period are requested to contact and return to the clinic for an examination as soon as possible. That examination includes a genital examination, and for women may include an internal genital examination.

In case of a recurrence, participants will be instructed to apply their usual treatment or refer to their treating physician whichever is applicable, in order to receive treatment per standard practice. If the subject is successfully treated within 21 days, and meets the inclusion criteria and none of the exclusion criteria, subject may re-enter the study. The concerning follow-up period is prolonged with the number of days the treatment required. These visits shall be recorded as an unscheduled visit.

In case of a second recurrence, the subject shall exit the study.

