### 4.2 Secondary Efficacy Endpoints

#### 4.2.1 Definition

Within-participant HSV-2 DNA detection rate on days with asymptomatic shedding For each person, the number of swabs on which shedding occurs only pre-intervention will be assessed, and then the number of swabs on which shedding occurs only postintervention will be subtracted. It will be tested whether the number of swabs on which shedding occurs only pre-intervention is the same when compared to the number of swabs on which shedding occurs only post-intervention.

HSV-2 copy number on HSV DNA positive samples detected by quantitative real-time PCR For each person, the mean PCR HSV-2 copy number on days with asymptomatic shedding occurring only pre-intervention will be calculated, and then the mean PCR HSV-2 copy number on days with asymptomatic shedding occurring only post-intervention will be subtracted. It will be tested whether the HSV-2 copy number on which shedding occurs only pre-intervention is the same when compared to the HSV-2 copy number on which shedding occurs only post-intervention.

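### The exploratory sex comparison of blocking ranks an undivided swab count, which cannot separate blocking from shedding frequency or days sampled

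*SAP*

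**What the plan says.** SAP 4.3.2 introduces the sub-analysis as exploring the cream's "blocking ability in relation to" sex, among other factors. Under Gender it specifies the method: "Between gender differences will be assessed for the secondary efficacy endpoints using the Wilcoxon rank-sum test". It adds: "Hodges-Lehmann estimates (point estimate and 95% exact confidence interval) will be used to assess the location of the shift between males and females".

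The detection endpoint is defined in SAP 4.2.1. For each person "the number of swabs on which shedding occurs only pre-intervention will be assessed", and the number positive only after application is subtracted. The endpoint is headed as a detection rate on days with asymptomatic shedding, but no division by days sampled or by positive days is stated. The sample-size section states the performance effect in relative terms: "40 participants taking samples for 28 days are needed to show a 50% reduction post-intervention".

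The protocol plans recruitment around this sub-analysis (section 4): "Therefore enrolment will be tracked to ensure enrolment of a minimum of 16 participants of the less represented sex".

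One other passage touches on sex, in SAP 4.2.2: "Exploratory Poisson regression analyses may also be performed exploring the effect of other covariates like center, age and gender". SAP 1.3 states that the exploratory sub-analyses, sex included, are descriptive and that no hypothesis is tested.

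**The concern.** Blocking is a relative quantity: the share of otherwise detectable virus that is no longer detected after application. The ranked quantity is an absolute count. A person who sheds more often, or is sampled on more days, gets a larger count for the same blocking. A rank-sum result on this count therefore cannot say whether the sexes differ in blocking, in shedding frequency or in days sampled. The reverse also holds, because a real difference in blocking can be hidden by an opposite difference in shedding.

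Days can differ between people. The As Treated Population needs only one application, missing values are not replaced, and after a first recurrence Protocol 5.2.6 says "The concerning follow-up period is prolonged with the number of days the treatment required".

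At stake is the interpretation of a subgroup analysis for which the protocol sets a recruitment floor.

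**Working it through.** **The plan's own figure.** There is no power statement for the sex comparison. The nearest figure is 40 participants for the overall signed-rank test, and the stated inputs do not fix its power. Simulated power at n = 40 (28 days, 8% falling to 4%) with independent swabs is 96.5% with no between-person variation, 91% at an intraclass correlation (ICC) of 0.3, 82% at 0.5 and 78% at 0.6. If a post-application positive requires a pre-application positive (the nested model), it is 91% to 100%. The present point does not depend on this figure. The 46 treated equals 40 × 1.15.

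**Inputs from the documents.** 28 days, 8% shedding and a 50% reduction (SAP 1.4); shedding on up to 25% of days (Protocol 1.2.2); a minimum of 16 of the less represented sex (Protocol 4), so 46 treated could split from 23/23 to 30/16; two-sided 5% (SAP 2.8).

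**Assumptions not in the documents.** ICC of shedding 0.2 (varied 0.1 to 0.3), swab sensitivity 0.8 (varied 0.7 to 0.9), and any shedding rate by sex.

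**Expected count.** Swabs positive both times cancel, so

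E(count) = days × (pre rate − post rate) = days × pre rate × relative reduction.

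- With 50% blocking throughout: 28 × 0.08 × 0.5 = 1.12; at 12%, 1.68; at 16%, 2.24; at 25%, 3.50.
- Masking: 28 × 0.08 × 0.80 = 1.79 and 28 × 0.16 × 0.40 = 1.79. The counts are equal although blocking differs twofold.

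**Relative index for comparison.** (Pre-only minus post-only) ÷ days with at least one positive swab, among people with such a day. At 50% blocking and sensitivity 0.8 its expected value is (0.8 − 0.4) ÷ (1 − 0.2 × 0.6) = 0.40 ÷ 0.88 = 0.455, so it is not the blocking fraction.

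**Rejection rates** (ICC 0.2, sensitivity 0.8, 28 days, pre and post swabs independent given a shedding day, tie-corrected rank-sum, 4,000 replicates):

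| Scenario | Count, 23/23 | Index, 23/23 | Count, 30/16 | Index, 30/16 |
|---|---|---|---|---|
| Equal 8% shedding, equal blocking | 5.2% | 4.5% | 4.8% | 4.6% |
| 9%/7% shedding, both 50% blocking | 7.8% | 5.4% | 6.2% | 4.7% |
| 10%/6% shedding, both 50% blocking | 15.2% | 5.2% | 13.3% | 5.9% |
| 8% shedding, 40% vs 80% blocking | 16.4% | 64.3% | 17.4% | 57.0% |
| 8% shedding, 40% vs 60% blocking | 8.9% | 18.6% | 8.8% | 18.6% |
| 10%/6% shedding, 40%/67% blocking | 4.8% | 31.0% | 5.0% | 27.2% |

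Repeat runs put 40% vs 80% on the count at 16% to 18%.

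**Sensitivity of these figures.**
- 40% vs 80% at ICC 0.1 and 0.3: count 26.8% and 12.4%, index 71.2% and 54.2%. If 8% is read as the swab detection rate at ICC 0.2: 21% and 72%. In the nested model with no between-person variation: 72% and 95%.
- Equal 50% blocking, nested model, ICC 0.1, 23/23, shedding of 8% vs 12%, 16% and 25%: the count rejects in about 19%, 56% and 97% of trials, the index in 4.7%, 5.1% and 7.0%.
- Days: 28 vs 26 gives 4.9%, and 28 vs 24 or 31 vs 26 gives 5.8%. At 28 vs 14 the result runs from about 12% (table settings) to 51% (nested, no between-person variation).
- The Hodges-Lehmann shift on the count is exactly 0, for 40% vs 80% at 8% shedding, in about 86–89% of trials at ICC 0.2 and 64–68% at ICC 0.1. At 25% shedding the figure is about 9% or less.

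**The case against.** The count is a legitimate absolute measure and matches the main endpoint, so using it again by sex is consistent. The analysis is exploratory, and with equal shedding and equal days the test has its nominal size. This all stands. It does not make the count a measure of blocking, which is what SAP 4.3.2 says it explores. The Poisson regression does not close the gap: it is optional and states no outcome, offset or sex-by-swab term.

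Some stronger readings are tempting but not supported:

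- **That the comparison will produce a false sex difference.** This needs the sexes to differ in shedding or in days sampled. The documents give 8% and up to 25% of days, neither by sex, so every sex-specific rate above is an assumption.
- **That the Hodges-Lehmann estimate is always zero, or that half of participants must score zero.** Both depend on shedding rate, ICC and sensitivity.
- **That unequal days can be ignored.** Small differences matter little in the runs above, but large ones can matter a great deal, depending on the model.
- **That the copy-number comparison is free of the problem.** Per-person means remove the day count, but the result is still an absolute difference that scales with baseline copy number.

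The relative index also has a real cost. It selects people on an observed outcome, whereas SAP 4.3.2 bases exploratory analyses on the whole As Treated Population.

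**Conclusion.** The concern holds in a limited form. For the detection endpoint, the planned sex comparison cannot separate blocking from shedding frequency or days sampled. This follows from the definition and needs no outside figure. The sizes are conditional: at ICC 0.2, sensitivity 0.8, 8% shedding and 23 per sex, a 40% vs 80% difference in blocking is found in about 16–18% of trials, compared with 64% on the index. An assumed 10%/6% shedding difference with equal blocking gives false differences in about 15%, compared with 5%. Neither measure is informative for moderate differences.

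Separately, SAP 1.3 and 4.3.2 contradict each other on whether a test is done.

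A reader might infer that the trial's performance result is compromised. It is not: the primary analysis of serious adverse device effects and the overall within-person signed-rank test are unaffected. The change is optional.

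**What to change.** Amend SAP 4.3.2 to tabulate by sex, for the As Treated Population: days sampled, pre- and post-application detection rates, and the relative reduction (1 − post rate ÷ pre rate). Keep the count difference as a descriptive summary and state that it is not read as blocking.

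Then reconcile SAP 1.3 with 4.3.2 in one of two ways:

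- **(a)** Delete the test for the detection endpoint by sex. This is the simpler option and fits SAP 1.3 as written.
- **(b)** Keep one exploratory test, with no success criterion, on (pre-only minus post-only) ÷ days with at least one positive swab, among participants with such a day, using a permutation p-value. Call it a relative index, not the blocking fraction, and except it from the no-testing statement in SAP 1.3.

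The copy-number comparison by sex also carries a rank-sum test, so SAP 1.3 must cover it under either choice.

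The cost is SAP wording and programming, with no new data. Option (b) loses participants with no positive day: roughly 30–60% of each sex at 8% shedding, depending on ICC and sensitivity. At 30/16 about 8 of the less represented sex would remain. It also stays weak for moderate differences, at about 19% for 40% vs 60%.
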